### 3.1.2.1 Definition of Dose-Limiting Toxicity

In this study, a DLT is defined as at least one of the following events occurring during the first cycle (*or the first two cycles in the bridging cohorts for patients with FL who start idasanutlin at Cycle 2*) of treatment and assessed by the investigator as not clearly related to the patient's underlying disease:

- *Any Grade 5 adverse event unless unequivocally due to the underlying malignancy or extraneous causes*
- Adverse event of any grade that leads to a delay of more than 14 days in the start of the next treatment cycle
- Grade 3 or 4 non-hematologic adverse event, with the following exceptions:
  - Grade 3 or 4 IRRs
    - Note that IRRs are not dose-dependent events. They may occur even after a small amount of drug has been administered.
    - Grade 3 diarrhea that responds to adequate therapy within 48 hours
    - Grade 3 nausea or vomiting that occurs in the absence of premedication and responds to adequate therapy within 72 hours
- *Any increase in hepatic transaminase > 3 • baseline and an increase in direct bilirubin > 2 • ULN, without any findings of cholestasis or jaundice or signs of hepatic dysfunction and in the absence of other contributory factors (e.g., worsening of metastatic disease or concomitant exposure to known hepatotoxic agent or of a documented infectious etiology) is suggestive of potential drug induced liver injury (according to Hy's Law) and will be considered a DLT*
- Hematologic adverse events that meet any of the following criteria:
  - Grade 3 or 4 neutropenia in the presence of sustained fever of >38°C (lasting >5 days) or a documented infection
  - Grade 4 neutropenia lasting >7 days
  - Grade 3 or 4 thrombocytopenia *if associated with Grade ≥ 3 bleeding*
  - Grade 4 thrombocytopenia lasting >7 days

Other toxicities that are considered clinically relevant and related to study treatment as determined by the investigator and the Medical Monitor may also be considered DLTs.

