**Table 19 Guidelines for Management of Non-Hematologic Toxicities**

Event	Action to Be Taken
General guidance for treatment delays and discontinuation	
 
When a treatment cycle is delayed because of toxicity resulting from any component of the regimen, all study treatment should be held and resumed together to remain synchronized.
 
If study treatment is withheld for > 21 days because of a toxicity that is attributable to study treatment, permanently discontinue study treatment.
 

IRRs and anaphylaxis	
 
Guidelines for the management of IRRs and anaphylaxis are provided in Section 5.1.1.1 and Appendix 9.
 
In case of Grade 4 IRRs or anaphylaxis, study treatment should be permanently discontinued.
 

TLS	
 
Withhold study treatment.a
 
Correct electrolyte abnormalities, monitor renal function and fluid balance, and administer supportive care, including dialysis as indicated.
 
If symptoms have resolved completely, resume obinutuzumab or rituximab and idasanutlin at full dose
 

New-onset neurologic manifestations suggestive of PML	
 
Withhold study treatment.a
 
Consult with a neurologist if PML is suspected (refer to Section 5.1.1.5 for guidance on investigations).
 
If PML is ruled out, resume obinutuzumab or rituximab and idasanutlin at full dose.
 
If PML is confirmed, permanently discontinue study treatment.
 

AST, ALT, or bilirubin increase: Grade • 3 (or • 10 • ULN for patients with liver involvement)	
 
Withhold study treatment.a
 
If improvement to Grade • 1 (or ≤ 5 • ULN (Grade 2) for patients with liver involvement), resume obinutuzumab or rituximab and idasanutlin at full dose for current and subsequent cycles.
 
Permanently discontinue study treatment for life-threatening liver toxicity (including Hy's Law cases).
 

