### **5.2.3 Adverse Events of Special Interest (Immediately Reportable to the Sponsor)**

Adverse events of special interest are required to be reported by the investigator to the Sponsor immediately (i.e., no more than 24 hours after learning of the event; see Section 5.4.2 for reporting instructions). Adverse events of special interest for this study include the following:

- Cases of potential drug-induced liver injury that include an elevated ALT or AST in combination with either an elevated bilirubin or clinical jaundice, as defined by Hy's Law (see Section 5.3.5.7)
- Suspected transmission of an infectious agent by study treatment, as defined below  
Any organism, virus, or infectious particle (e.g., prion protein transmitting transmissible spongiform encephalopathy), pathogenic or non-pathogenic, is considered an infectious agent. A transmission of an infectious agent may be suspected from clinical symptoms or laboratory findings that indicate an infection in a patient exposed to a medicinal product. This term applies only when a contamination of any of the study treatment components is suspected.
- TLS of any grade, irrespective of causality
- Grade • 3 neutropenia, including febrile neutropenia
- Grade • 2 diarrhea
- Grade • 3 thrombocytopenia or Grade 2 thrombocytopenia if associated with hemorrhage/bleeding
- *Grade • 2 Clostridium difficile infection*
- *Second malignancies*

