#### **5.3.5.7 Abnormal Liver Function Tests**

The finding of an elevated ALT or AST ( $> 3 \cdot$  baseline value) in combination with either an elevated total bilirubin ( $> 2 \cdot$  ULN) or clinical jaundice in the absence of cholestasis or other causes of hyperbilirubinemia is considered to be an indicator of severe liver injury (as defined by Hy's Law). Therefore, investigators must report as an adverse event the occurrence of either of the following:

- Treatment-emergent ALT or AST  $> 3 \cdot$  baseline value in combination with total bilirubin  $> 2 \cdot$  ULN (of which  $\cdot$  35% is direct bilirubin)
- Treatment-emergent ALT or AST  $> 3 \cdot$  baseline value in combination with clinical jaundice

The most appropriate diagnosis or (if a diagnosis cannot be established) the abnormal laboratory values should be recorded on the Adverse Event eCRF (see Section 5.3.5.2) and reported to the Sponsor immediately (i.e., no more than 24 hours after learning of the event), either as a serious adverse event or an adverse event of special interest (see Section 5.4.2).

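### The liver DLT rule in 3.1.2.1 leaves out jaundiced cases that 5.3.5.7 and 5.2.3 count as Hy's Law, so such a case below Grade 3 may go uncounted as a toxicity in the dose model

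*Combined protocol and SAP*

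**What the plan says.** Four places in the protocol deal with drug-induced liver injury.

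- **Section 3.1.2.1 (DLT definition).** A transaminase rise above 3 times baseline together with "an increase in direct bilirubin" above 2 times ULN "is suggestive of potential drug induced liver injury (according to Hy's Law) and will be considered a DLT". The bullet applies only "without any findings of cholestasis or jaundice or signs of hepatic dysfunction" and in the absence of other contributory factors.
- **Section 5.3.5.7 (abnormal liver tests).** Hy's Law is ALT or AST above 3 times baseline "in combination with either an elevated total bilirubin" above 2 times ULN "or clinical jaundice in the absence of cholestasis or other causes of hyperbilirubinemia". The second of its two reporting criteria is a transaminase above 3 times "baseline value in combination with clinical jaundice".
- **Section 5.2.3 (adverse events of special interest).** The list opens with "Cases of potential drug-induced liver injury that include an elevated ALT or AST in combination with either an elevated bilirubin or clinical jaundice", and refers to 5.3.5.7 for the definition.
- **Table 19.** The liver row reads "Permanently discontinue study treatment for life-threatening liver toxicity" and expressly includes Hy's Law cases.

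Three other routes in 3.1.2.1 can make a liver event a DLT. Two are mandatory: a Grade 3 or 4 non-hematologic event (no liver exception is listed), and an event of any grade that delays the next cycle by more than 14 days. The third is discretionary: the investigator and Medical Monitor may count other clinically relevant, treatment-related toxicities.

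Section 3.1.2.3 bases the dose model on whether a DLT occurs.

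**The concern.** Jaundice brings a case into Hy's Law in 5.3.5.7 and 5.2.3 and takes it out of the DLT bullet in 3.1.2.1, although that bullet names Hy's Law as its basis. Signs of hepatic dysfunction are likewise a ground for leaving the bullet, and 5.3.5.7 does not mention them. As written, the mandatory liver rule omits the clinically more overt cases.

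The binary DLT outcome is the only toxicity variable in the mCRM likelihood. A patient reported as a Hy's Law case within 24 hours, and listed in Table 19 for permanent discontinuation, could still contribute no toxicity to the posterior from which the next dose and the MTD are derived. Section 5.1.3 lists liver test abnormalities as a potential risk of idasanutlin, so the case is not purely hypothetical.

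**Working it through.** **1. The definitions side by side**

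| Element | 3.1.2.1, DLT bullet | 5.3.5.7, Hy's Law | 5.2.3, special interest |
|---|---|---|---|
| Transaminase | > 3 × baseline | > 3 × baseline | elevated, per 5.3.5.7 |
| Bilirubin | direct > 2 × ULN, required | total > 2 × ULN, or jaundice instead | elevated, or jaundice instead |
| Clinical jaundice | removes the case | qualifies the case | qualifies the case |
| Signs of hepatic dysfunction | remove the case | not mentioned | not mentioned |
| Cholestasis | excluded | excluded | per 5.3.5.7 |

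The cholestasis exclusion is shared and is not in dispute. The conflict lies in the jaundice and hepatic-dysfunction rows.

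**2. Can another DLT route catch the jaundiced case?**

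- *Grade 3 or 4.* Yes, if the event is graded that high. However, 3 × baseline is not a grade limit. Table 19, in its line for patients with liver involvement, labels values up to 5 × ULN as Grade 2, so at least there a qualifying transaminase can lie below Grade 3. The full CTCAE limits are not in the documents, so the size of the sub-Grade-3 group cannot be worked out.
- *Delay of more than 14 days.* Possibly. The text does not say whether permanent discontinuation counts as a delay of the next cycle.
- *Discretionary clause.* It permits counting the case but does not require it.

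**3. What happens to a patient who is not counted?**

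Section 3.1.2 makes a patient who leaves the study during the DLT window for a reason other than a DLT non-evaluable and replaced. It also replaces a patient who misses a dose in the window for such a reason. Section 4.6.2 replaces patients who stop treatment before completing Cycle 1 only if the reason is not toxicity. The two rules therefore differ for a toxicity discontinuation that is not a DLT. If the event arises after the last dose in the window and the patient stays in the study, neither rule removes the patient, who is scored as no DLT. On each path the event is not counted as a toxicity.

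**4. Effect on the next dose**

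The protocol's figures for cohorts of 3 (Section 3.1.2.3 text and Table 5), with no DLT in earlier cohorts:

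| Cohort dose | 0 DLT | 1 DLT | 2 DLTs | 3 DLTs |
|---|---|---|---|---|
| 100 mg | 250 | 100 | 50 | 50 |
| 250 mg | 300 | 250 | 200 | 100 |
| 300 mg (first) | 300 | 300 | not needed | not needed |

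To check them, the model logit p(d) = log α + β·log(d/300) was integrated on a grid. The inputs were log α ~ N(−1.237, variance 2.661), log β ~ N(0.460, variance 1.816), doses from 50 to 800 mg in steps of 50, the stated increment caps, and minimum expected loss with weights [1, 0, 1, 2]. This reproduces 9 of these 10 recommendations. The exception is 3 of 3 DLTs at 250 mg (stated 100 mg, computed 150 mg), which is not used here.

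If one true DLT is not counted, and it is the only one in its cohort:

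- 100 mg cohort: 250 mg instead of 100 mg, a difference of 250 − 100 = 150 mg.
- 250 mg cohort: 300 mg instead of 250 mg, a difference of 300 − 250 = 50 mg.
- First 300 mg cohort: 300 mg either way, a difference of 0.

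If the patient in the 250 mg cohort is dropped instead (0 of 2, before replacement), the model still gives 300 mg.

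**5. Direct versus total bilirubin**

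The first reporting criterion in 5.3.5.7 requires total bilirubin > 2 × ULN(total) with a 35% direct share. The comparison sign is lost in the text and is read here as at least 35%. Then direct > 0.35 × 2 = 0.70 × ULN(total). The DLT bullet needs direct > 2 × ULN(direct). With r = ULN(direct)/ULN(total), this is guaranteed when 2r ≤ 0.70, that is r ≤ 0.35. The documents give no ULNs, so r is an assumption:

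- r from 0.15 to 0.35: no case escapes on this ground.
- r = 0.40: at a 35% direct share, cases escape for total between 2.0 and 2 × 0.40/0.35 = 2.29 × ULN.
- r = 0.50: the same holds up to 2 × 0.50/0.35 = 2.86 × ULN.

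**The case against.** The best reply is that the gap is narrow and that people stand between the model and the dose.

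- *Severity.* Section 5.3.5.7 calls a Hy's Law finding an indicator of severe injury, and Table 19 groups it with life-threatening toxicity. Section 5.3.5.7 asks for a diagnosis to be recorded where one can be made, and Table 21 grades severe events as 3 and life-threatening ones as 4 for terms not listed in CTCAE. Many such cases may therefore be Grade 3 or 4, and so DLTs. This stands for those cases, but no text says that every Hy's Law case is Grade 3 or 4.
- *Delay.* A patient taken off treatment does not start the next cycle on time, so the 14-day bullet arguably applies. That is a reasonable reading, but the protocol does not state it.
- *Oversight.* The sponsor learns of the case within 24 hours, each dose decision weighs adverse-event and laboratory data, clinical judgment overrides the mCRM, and the RP2D takes in all safety data. All of this stands and limits the harm. It does not correct the DLT count that enters the posterior and the MTD estimate.
- *Likelihood.* Liver abnormalities are only a potential risk of idasanutlin, and Section 1.4 names thrombocytopenia and neutropenia as the main DLTs. The documents give no basis for a frequency, and none is claimed.

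**Conclusion.** The contradiction on jaundice and hepatic dysfunction is in the current protocol text and should be resolved. It leaves a specific gap: a Hy's Law case with jaundice, below Grade 3 and not captured by the 14-day-delay bullet, is a DLT only by discretion. One such case can change the model's next recommendation by 150 mg after the 100 mg cohort or 50 mg after the 250 mg cohort, and by nothing at the first 300 mg cohort. These figures assume a cohort of 3, no earlier DLT, and no clinical override.

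A reader might infer more than the documents support:

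- *That liver injury in general escapes DLT counting.* It does not, because the Grade 3 or 4 and delay bullets remain mandatory. Table 19's Grade 2 label for values up to 5 × ULN is written for patients with liver involvement and should not be stretched to all patients.
- *That every missed case is entered as no DLT and drives the MTD up.* Some would be non-evaluable and replaced under 3.1.2, and the final dose decision is not the model's alone.
- *That the direct-versus-total difference is a second gap of equal weight.* It matters only if a local ULN ratio exceeds about 0.35, an assumption the documents cannot settle.

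**What to change.** Reconcile Section 3.1.2.1 with Sections 5.3.5.7 and 5.2.3 and Table 19, so that one liver-injury definition, covering the role of jaundice and hepatic dysfunction and the bilirubin fraction, governs DLT counting, special-interest reporting and discontinuation. In the same edit, state whether permanent discontinuation counts under the 14-day-delay bullet, and align Sections 3.1.2 and 4.6.2 on whether a patient who stops for a toxicity that is not a DLT is evaluable, replaced or neither. The sponsor decides which wording holds; no clinical threshold is proposed here.

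The cost is protocol wording only, with no change to the model, the sample size or the assessments: Section 4.5.6.1 already collects both total and direct bilirubin. Any Hy's Law case already observed in a DLT window should be checked against the reconciled rule before the next model update.

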### **3.1.2            Dose-Escalation Phase (Part 1)**

The purpose of the dose-escalation phase (Part 1) is to identify the RP2D *and regimen* for idasanutlin when combined with a fixed dose of 1000 mg of obinutuzumab in patients with R/R FL and *the RP2D for idasanutlin when combined with 375 mg/m^2 of rituximab in patients with R/R DLBCL*. The RP2D will be based on MTD of idasanutlin when combined with a fixed dose of obinutuzumab *or with 375 mg/m^2 of rituximab*, but will also include all safety data during treatment. *There could be two different RP2Ds and/or regimens dependent on the combinations of idasanutlin plus obinutuzumab or idasanutlin plus rituximab.*

During the escalation phase, approximately 9• 40 patients will be enrolled in dosing groups of 3• 6 patients each and will be treated at escalating doses of idasanutlin in accordance with the treatment regimen and dose-escalation rules described in Section 3.1.2.2.

Patients will be closely monitored for adverse events during a DLT assessment window, defined as the first treatment cycle *for Regimen A and the first two treatment cycles (one cycle of idasanutlin combination treatment) for patients enrolled in bridging cohort(s) in which idasanutlin will start at Cycle 2 (Regimen B)*. See Section 3.1.2.2 for treatment regimens. Adverse events meeting the criteria for DLT, as defined below (see Section 3.1.2.1), will be reported to the Sponsor within 24 hours (see Section 5.4.2).

Patients experiencing a DLT during the *DLT window* will permanently discontinue study treatment.

Patients who discontinue from the study prior to completing the DLT assessment window for reasons other than a DLT will be considered non-evaluable for dose-escalation decisions and MTD assessments and will be replaced by an additional patient at that same dose level who has not been previously treated in the study. Patients who miss one or more doses of obinutuzumab, *rituximab*, or idasanutlin during the DLT assessment window for reasons other than a DLT will also be replaced.

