**Table 2 Induction Treatment for Dose-Escalation Phase**

Dose-Escalation, FL and DLBCL Patients (28-Day Cycles): Regimen A	
Cycle 1	DLT period 
 
• Obinutuzumab 1000 mg IV on Days 1, 8, and 15
 
• Idasanutlin, oral Days 1•5, starting dose 100 mg QD, minimal clinically and pharmacologically feasible dose-escalation steps 50 mg
 

Cycles 2•6	
 
• Obinutuzumab 1000 mg IV on Day 1
 
• Idasanutlin, oral Days 1•5, starting dose 100 mg QD
 

Dose-Escalation Bridging Cohort, DLBCL Patients Only (28-Day Cycles)	
Cycle 1	DLT period 
 
• Rituximab 375 mg/m^2 IV on Day 1
 
• Idasanutlin, oral Days 1•5, starting dose MTD identified in combination with obinutuzumab with Regimen A, minimal clinically and pharmacologically feasible dose-escalation steps 50 mg
 

Cycles 2–6	
 
• Rituximab 375 mg/m^2 IV on Day 1
 
• Idasanutlin, oral Days 1•5, starting dose MTD identified in combination with obinutuzumab
 

Dose-Escalation Bridging Cohort, FL Patients Only (28-Day Cycles): Regimen B	
Cycle 1	
 
• Obinutuzumab 1000 mg IV on Days 1, 8, and 15
 

Cycles 2–6	
 
• Obinutuzumab 1000 mg IV on Day 1
 
• Idasanutlin, oral Days 1•5, starting dose MTD identified in combination with obinutuzumab with Regimen A during dose escalation, minimal clinically and pharmacologically feasible dose-escalation steps 50 mg
 

DLT period will be Cycles 1 and 2.	

*DLBCL =diffuse large B-cell lymphoma; DLT = dose-limiting toxicity; FL =follicular lymphoma; IV=intravenous; MTD =maximum tolerated dose; QD=once a day.*

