### **4.4.1 Permitted Therapy**

Premedication is permitted as described in Section 4.3.2.6.

Patients who use oral contraceptives, hormone-replacement therapy, or other maintenance therapy should continue their use.

During the dose-escalation phase, granulocyte colony-stimulating factor (G-CSF) is not permitted during the first cycle, unless the patient experiences a DLT of neutropenia.

During the expansion phase, G-CSF is permitted as clinically indicated per American Society of Clinical Oncology (ASCO), European Organization for Research and

Treatment of Cancer (EORTC), and European Society for Medical Oncology (ESMO) guidelines (Smith et al. 2006) or per each site's institutional standards.

Prophylactic treatment with antibiotics should be administered per standard of care.

Necessary supportive measures for optimal medical care will be given throughout the study according to institutional standards.

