### 5.1.5.1 Toxicities during Induction Treatment Hematologic Toxicities

Table 17 provides guidelines for management of hematologic toxicities that occur during induction treatment, with the exception of Days 8 and 15 of Cycle 1. Table 18 provides guidelines for management of hematologic toxicities that occur on Days 8 and 15 of Cycle 1, when patients are to receive treatment with obinutuzumab only. Hematologic toxicity is defined as neutropenia, anemia, or thrombocytopenia. Lymphopenia is not considered hematologic toxicity but an expected outcome of therapy.

**Table 17 Guidelines for Management of Hematologic Toxicities That Occur during Induction Treatment (Except for Days 8 and 15 of Cycle 1)**

Event	Action to Be Taken

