Grade 3 or 4 hematologic toxicity a, b	
For patients who have had one, two, or no prior dose reductions:
 
 
• Withhold study treatment.a
 
• Administer RBCs or platelets as required.
 
• If patient has not already initiated G-CSF, initiate prophylactic G-CSF for current and subsequent cycles.
 
• If improvement to Grade • 2 or baseline • 14 days after the scheduled date for the next cycle, resume obinutuzumab or rituximab at full dose and resume idasanutlin at current dose.
 
• If improvement to Grade • 2 or baseline 15• 21 days after the scheduled date for the next cycle, resume obinutuzumab or rituximab at full dose and resume idasanutlin at a reduced dose according to guidelines in Section 5.1.5 for current and subsequent cycles.
 
• If study treatment is withheld for >21 days, permanently discontinue study treatment.
 
• Permanently discontinue study treatment if any of the following events occur: 
 
Grade 3 or 4 thrombocytopenia of any duration if associated with Grade ≥ 3 bleeding
 
Recurrent Grade 3 or 4 neutropenia associated with fever of > 38°C (> 5 days) or a documented infection despite use of G-CSF and after one idasanutlin dose reduction
 
Recurrent Grade 4 neutropenia or thrombocytopenia lasting more than 7 days despite use of G-CSF (for neutropenia) and after one idasanutlin dose reduction
 
 
 
 
For patients who have had three prior dose reductions or for patients who reach the lowest dose level and no further dose reduction is applicable (see Section 5.1.5):
 
 
• Permanently discontinue study treatment.
 

G-CSF = granulocyte colony-stimulating factor; NHL = non-Hodgkin's lymphoma.

a Treatment delays apply to all toxicities; dose modifications apply only to toxicities that are considered to be related to idasanutlin

b If cytopenia is thought to be caused mainly by NHL infiltration of the bone marrow, the investigator may decide not to modify dose.

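### The G-CSF bar in dose escalation covers only Cycle 1, so Regimen B's first idasanutlin cycle is scored for prolonged neutropenia while G-CSF is allowed

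*Combined protocol and SAP*

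**What the plan says.** Section 3.1.2.1 lists "Grade 4 neutropenia lasting >7 days" among the hematologic DLTs, alongside the matching platelet criterion, "Grade 4 thrombocytopenia lasting >7 days".

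Section 4.4.1 states that in dose escalation G-CSF "is not permitted during the first cycle, unless the patient experiences a DLT of neutropenia". The limit is a cycle number, not the DLT window.

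Sections 3.1.2 and 3.1.2.2 give Regimen B obinutuzumab alone in Cycle 1, with idasanutlin added from Cycle 2. Table 2 adds: "DLT period will be Cycles 1 and 2".

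Section 5.1.5.1 describes Table 17 as "guidelines for management of hematologic toxicities that occur during induction treatment, with the exception of Days 8 and 15 of Cycle 1". At Grade 3 or 4 hematologic toxicity the table instructs: "If patient has not already initiated G-CSF, initiate prophylactic G-CSF for current and subsequent cycles". Section 5.1.3.2 also encourages growth factors, particularly after a first neutropenia of Grade 3 or higher.

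Section 3.3.3 gives the purpose of Regimen B as easing the hematologic toxicity seen when both drugs start together, and says that one regimen only will go to expansion.

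**The concern.** A DLT defined by duration measures the drug only if rescue during the window is controlled. In Regimen B the bar applies to the cycle without idasanutlin and ends before the cycle that the DLT assessment is mainly about. G-CSF started in Cycle 2 as Table 17 directs can turn a Grade 4 neutropenia of more than 7 days into a shorter one that is not a listed DLT.

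Two things are at stake. The mCRM is updated on DLT occurrence, and Section 3.1.2.3 says a similar mCRM will support Regimen B, so an uncounted DLT can raise the next recommended dose. And the choice between regimens rests partly on hematologic tolerability, which would be observed without G-CSF in Regimen A's first idasanutlin cycle and with G-CSF allowed in Regimen B's.

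**Working it through.** **Step 1: rules by regimen, first idasanutlin cycle in escalation**

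| | Regimen A | Rituximab bridging | Regimen B |
|---|---|---|---|
| First idasanutlin cycle | 1 | 1 | 2 |
| DLT window | Cycle 1 | Cycle 1 | Cycles 1 and 2 |
| G-CSF barred in that cycle (4.4.1) | yes | yes | no |
| Table 17 G-CSF instruction applies | yields to 4.4.1 | yields to 4.4.1 | yes |

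Only Regimen B is affected. The amendment's list of changes shows Cycle 1 wording replaced by the DLT window in Sections 3.1.2 and 4.6.2, but no change to 4.4.1. That suggests the phrase was left over when Regimen B was added.

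**Step 2: what one uncounted DLT does in the printed example**

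Inputs are in Section 3.1.2.3: logit p(d) = log(alpha) + beta·log(d/300); log(alpha) ~ N(-1.237, variance 2.661) and log(beta) ~ N(0.460, variance 1.816), uncorrelated; loss [1,0,1,2] for DLT rates of 0–25, 25–35, 35–60 and 60–100%; probability of a rate above 35% below 35%; printed caps on increments.

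The printed next dose, after 0/3 at 100 mg and then 0, 1 or 2 DLTs in 3 at 250 mg, is 300, 250 or 200 mg. A grid posterior with minimum expected loss reproduces all three. P(DLT rate >35%) at 300 mg is 0.12 after 0/3 and 0.38 after 1/3, on either side of the 35% limit. One uncounted DLT therefore moves the recommendation from 250 to 300 mg.

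The reproduction is not exact throughout. Comparing the 0-DLT and 1-DLT cells over the ten printed rows, both match in six; elsewhere the difference is at most 50 mg.

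**Step 3: a first Regimen B cohort with Regimen A data carried over**

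The protocol does not say whether Regimen A data enter the Regimen B model, so the data below are assumed. Each set is one for which the loss rule itself recommends the dose at which Regimen B would open.

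| Assumed Regimen A data | Regimen B dose | Next dose, 0/3 counted | Next dose, 1/3 counted |
|---|---|---|---|
| 0/3 at 100, 2/3 at 250, 1/6 at 200 mg | 200 mg | 250 mg | 200 mg |
| 0/3 at 100, 2/6 at 250 mg | 250 mg | 250 mg | 250 mg |
| 0/3 at 100, 0/3 at 250, 1/6 at 300 mg | 300 mg | 300 mg | 300 mg |
| 0/3 at 100, 0/3 at 250, 2/6 at 300 mg | 300 mg | 300 mg | 300 mg |

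The dose changes in one case of four. If the rule instead maximises the target-interval probability under the same overdose limit, the second row becomes 300 versus 250 mg. The effect depends on the data and on how the rule is read.

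**The case against.** **A model that uses DLT counts must respond when a count changes.** Step 2 therefore shows sensitivity, not that the event will occur. This stands: the documents give no frequency for neutropenia shortened by G-CSF below the 7-day limit.

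**Other protections exist.** Neutropenia with sustained fever or infection, a delay of more than 14 days, and the Grade 5 and non-hematologic DLTs still count. The investigator and Medical Monitor may call other events DLTs (3.1.2.1). Laboratory data are reviewed at each dose decision (3.1.2.2), clinical judgment overrides the model (3.1.2.3), and neutropenia of Grade 3 or higher is reported within 24 hours (5.2.3). Regimen B also opens at a dose already identified as the MTD under Regimen A's bar, and going higher is optional. These points limit the harm. They do not restore the duration criterion: the catch-all clause is discretionary, and the other measures make an event visible without scoring it.

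**Stronger readings that a reader might infer:**

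- *Regimen B's MTD will be too high.* With the printed prior alone and assumed opening doses of 150, 200, 250, 300 or 350 mg, 0/3 instead of 1/3 raises the next dose in all five cases. That requires the Regimen B model to ignore every Regimen A patient, which the protocol does not say.
- *The bar also fails in Regimen A,* because Table 17 and Sections 5.1.1.3 and 5.1.3.2 carry no exception. Section 4.4.1 is the specific rule, and 5.1.1.3 refers to it for prophylaxis, so the ordinary reading is that the bar holds.
- *Transfusion hides platelet DLTs in every cohort.* Table 17 says "Administer RBCs or platelets as required", and no text says how a transfused count bears on "Grade 4 thrombocytopenia lasting >7 days". But silence is not an instruction to score it as recovery. The catch-all clause, 24-hour reporting of thrombocytopenia of Grade 3 or higher, and adverse event reporting of laboratory changes that need intervention (5.3.5.5) give partial cover. This is a clarification, not a defect of the same weight.

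**Conclusion.** The point holds for Regimen B and G-CSF, on the text alone. The bar is defined by a cycle number that does not match the Regimen B window, and Table 17 directs the use of G-CSF in the cycle left open. Regimen A and the rituximab bridging cohort are not affected.

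The effect on dose is conditional. One uncounted DLT in three raises the next recommendation by 50 mg in the printed 250 mg example and in the assumed 200 mg carry-over case; it changes nothing in the other three carry-over cases under the loss rule. These results assume the printed prior, the loss rule and the carry-over data shown, because the Regimen B model is described only as similar. Upward bias of the MTD is possible but not shown. The unequal rescue rules between the two regimens need no such assumption.

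The change should be made before the Regimen B cohort opens.

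**What to change.** In Section 4.4.1 replace *during the first cycle* with *during the DLT window*, and keep the exception for a patient who already has a neutropenia DLT. In Table 17 and Sections 5.1.1.3 and 5.1.3.2 add: *except during the DLT window in dose escalation; see Section 4.4.1*.

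The cost is a few words and three cross-references. Regimen B is introduced by this amendment, so no patient enrolled before it is affected. The clinical downside is that Regimen B patients with uncomplicated Grade 4 neutropenia of up to 7 days would go without G-CSF in Cycle 2, as Regimen A patients already do in Cycle 1.

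Optional clarification: state in Section 3.1.2.1 that a platelet count supported by transfusion does not by itself end a Grade 4 episode for DLT scoring. This could score as DLTs some patients who would have recovered within 7 days, and it may need transfusion dates and extra counts.
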